9.1. Adverse Events

AEs will be mapped to SOCs and PTs using the MedDRA Version 19 or later. AEs will be monitored during the study and the data analyzed with respect to overall incidence as well as severity and potential relationship of AEs to study medication.

A treatment-emergent AE (TEAE) is defined as an AE that meets any of the following conditions:

- begins on or after the first dose of study drug and before the stop of study drug + 28 days;
- begins before the first dose of study drug and worsens in severity on or after the first dose of study drug and before the stop of study drug + 28 days;
- is completely missing an onset date and end date;
- is completely missing an onset date and the end date is on or after the first dose of study drug.

For the purpose of inclusion in TEAE tables, incomplete AE onset and end dates will be imputed as follows:

Missing onset dates (where UK and UKN indicate unknown or missing day and month respectively):

- UK-MMM-YYYY: If the month and year are different from the month and year of the first dose of study drug, assume 01-MMM-YYYY. If the month and year are the same as the first dose of study drug month and year, and the end date (after any imputation) is on or after the first dose of study drug, then assume the date of the first dose of study drug. If the month and year are the same as the first dose of study drug month, and year and the end date (after any imputation) is prior to the first dose of study drug, then assume the end date for the onset date.
- DD-UKN-YYYY/UK-UKN-YYYY: If the year is different from the year of first dose of study drug, assume 01-JAN-YYYY of the collected year. If the year is the same as the first dose of study drug year, and the end date (after any imputation) is on or after the first dose of study drug, then assume the date of the first dose of study drug. If the year is the same as the first dose of study drug, and the end date (after any imputation) is prior to the first dose of study drug, then assume the end date for the onset date.

Missing end dates (where UK and UKN indicate unknown or missing day and month respectively):

- UK-MMM-YYYY: Assume the last day of the month;
- DD-UKN-YYYY/UK-UKN-YYYY: Assume 31-DEC-YYYY.

An overview summary of the number and percentage of subjects with any TEAE, serious TEAE, study drug-related TEAE, study drug-related serious TEAE, TEAE leading to treatment discontinuation, TEAE leading to study termination, TEAE leading to treatment interruption and AE leading to death will be provided.

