Exploratory endpoints include the proportion of subjects achieving an LVOT gradient response of post-exercise peak gradient < 10 mm Hg; change from baseline to Week 12 in NYHA functional class, NT-proBNP, and KCCQ OSS; change from baseline in arterial pulse wave morphology assessed using an optical biosensor; and change from baseline in heart rate and heart rhythm as assessed using a cardiac monitoring skin patch.

Safety endpoints include treatment-emergent AEs and serious adverse events (SAEs), and changes from baseline in laboratory test results, vital signs, and ECGs. Any abnormal ECG or vital sign finding judged by the investigator to be clinically important will be recorded as an AE.

End of Study

Subjects will be followed through completion of End of Study (EOS) procedures. All AEs, including SAEs and deaths, will be collected for the duration of the study, up to and including the EOS visit.

If there is a significant clinical abnormality or a clinically significant laboratory abnormality in need of monitoring, the subject will be followed until resolution of the abnormality or until it is considered stable in the opinion of the investigator.

Sample Size and Statistical Considerations:

Sample Size:

Approximately 10 subjects will be dosed in Part A and approximately 10 in Part B. The sample size is based on practical considerations and is consistent with this type of study. Ten subjects receiving MYK-461 will provide 80% power to detect a 30 mm Hg difference versus baseline in post-exercise LVOT peak gradient and a > 99% power to detect a 50 mm Hg difference. This assumes a 1-sided $\alpha = 0.05$ and a common standard deviation of 35 mm Hg.

Statistical Analyses:

All efficacy and PD analyses will be performed on the Efficacy/PD Analysis Population, which comprises all subjects who receive at least 1 dose of MYK-461 and have primary or secondary endpoint data, including a baseline value and at least one post baseline value measured during the on-treatment period.

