9.2 Pharmacokinetic, Pharmacogenetic, and Biomarker Assessments

9.2.1 Pharmacokinetic Assessments

Blood samples will be collected for PK assessments at all post-Screening visits. Plasma concentrations of MYK-461 will be evaluated. Unscheduled or additional PK samples may be collected if appropriate in the opinion of the investigator and/or Sponsor.

At all visits from Day 1 to Week 12 (inclusive), MYK-461 will be administered at the investigational site to facilitate collection of PK samples \leq 2 hours prior to dosing.

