9.5.6 Week 12/Early Termination

- Complete physical examination; includes neurological examination and weight
- 12-lead ECG (triplicate)
- Vital signs after resting for at least 5 minutes
- Resting TTE
- Hemodynamic stress echocardiography after 4 hour fast
- CPET after a 4-hour fast (water is allowed). CPET may be conducted at the Week 12 visit or anytime between Weeks 10 and 12. If CPET and hemodynamic stress echocardiography are conducted at the same visit, the hemodynamic stress echocardiography should be conducted first, followed by the CPET.
- Blood samples for
 - Hematology and serum chemistry
 - NT-proBNP
 - Potential exploratory biomarker analysis
 - PK (within ≤ 2 hours prior to dosing)
- Pregnancy test (blood or urine) for women of childbearing potential, based on standard at institution
- Urine sample for urinalysis
- Retrieve previously applied cardiac monitoring skin patch and apply a new patch. The skin patch is only required for up to 2 weeks of wear time.
- Optical biosensor pulse wave analysis (consenting subjects)
- Concomitant therapy assessment
- AE assessment
- Study medication compliance
- Dyspnea NRS
- KCCQ
- NYHA class
- Open-label MYK-461 administration at site

9.5.7 ***Week 16/End of Study***

- Complete physical examination; includes neurological examination and weight
- 12-lead ECG (triplicate)
- Vital signs after resting for at least 5 minutes
- Resting TTE
- Hemodynamic stress echocardiography after 4 hour fast
- Blood samples for
 - Hematology and serum chemistry
 - NT-proBNP
 - PK
- Urine sample for urinalysis
- Pregnancy test (blood or urine) for women of childbearing potential, based on standard at institution
- Retrieve cardiac monitoring skin patch
- Optical biosensor pulse wave analysis (consenting subjects)
- Concomitant therapy assessment
- AE assessment
- Dyspnea NRS
- KCCQ
- NYHA class

9.5.8 ***Unscheduled Visits***

At the investigator's discretion, unscheduled visits may be conducted for the assessment of AEs, physical examinations, vital signs, laboratory tests, ECGs, and/or TTEs. All information collected from unscheduled visits will be recorded on the eCRF and included in the clinical database.

9.6 **Visit Window and Missed Visits**

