11.3.8.1 Adverse Events

AEs will be mapped to system organ classes and preferred terms using the Medical Dictionary for Regulatory Activities (MedDRA). AEs will be monitored during the study and the data analyzed with respect to overall incidence as well as severity and potential relationship of AEs to study medication. AEs with onset on or after the first dose of study medication, or with an onset before the first dose of study medication that increase in severity on or after the first dose of study medication, will be considered treatment-emergent. Treatment-emergent AEs will be summarized for the Safety Analysis Population by system organ class and preferred term, and by severity and relationship to treatment. Severe and life-threatening AEs, SAEs, and AEs leading to study withdrawal, if any, will be presented in data listings.

11.3.8.2 12-lead Electrocardiogram

The RR, PR, QRS, and QT intervals will be measured. HR will be calculated as $60/(RR \times 1000)$ (with RR expressed in msec) and rounded to the nearest integer.

Correction for Heart Rate

Corrected QT interval (QTc) will be calculated using the manually over-read QT values. Each individual ECG QT value will be corrected for HR. The measured QT data will be corrected for HR using the Fridericia method (QTcF) as per the following formulae/method (with QT, RR and QTc expressed in msec):

Fridericia's Correction:

$$QT_{cF} = \frac{QT}{(RR / 1000)^{1/3}}$$

ECG Numeric Variables

HR, PR, QRS, and QTcF will be summarized using descriptive statistics. The change from baseline of these ECG parameters at each timepoint will be listed for each subject. For each timepoint of measurement, the changes from baseline will be summarized using descriptive statistics.

Categorical Analysis

The incidence count and percentage of subjects with any postdose QTcF values of > 450 msec, > 480 msec, and > 500 msec will be tabulated for all subjects. Subjects with QTc values > 500 msec will be listed with corresponding baseline values, Δ QTcF, and baseline and treatment HR. The incidence count and percentage of subjects with Δ QTcF increase of > 30 msec and > 60 msec will be tabulated.

Morphology Findings

New ECG morphologies for each subject not present on any ECG at baseline for that subject will be summarized for all observation timepoints combined.

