All analysis and summary tables will have the analysis population sample size (i.e., number of subjects) in the column heading. All listings will be sorted for presentation in order of study site, subject identification and date of procedure or event.

The day of the first dose of study drug will be defined as Day 1.

Baseline value will be defined as the last non-missing value in date/time before the first dose of study drug is administered.

Missing data handling will be described in Section 7, 8, 9 and 10.

All laboratory data will be reported using International System of Units (SI).

The planned analysis visit window for weekly visits will consider +/- 3 days of the scheduled visit date based on the date of first exposure to the study drug. For a missed visit, the evaluation will be rescheduled as close as possible to the original planned visit, thus analysis windows have been designed to be all-inclusive. If more than one result is available for a particular visit window and results are equidistant from the analysis target date, the later result will be selected to break the tie. The associated visit window with corresponding visit is tabulated below.

Visit	Scheduled Visit Day	Visit Window
Day 1	Day 1	[1, 4]
Week 1	Day 8	[5, 11]
Week 2	Day 15	[12, 18]
Week 3	Day 22	[19, 25]
Week 4	Day 29	[26, 32]
Week 5	Day 36	[33, 39]
Week 6	Day 43	[40, 46]
Week 7	Day 50	[47, 53]
Week 8	Day 57	[54, 64]
Week 10*	Day 71	[65, 78]
Week 12*	Day 85	[79, 99]
Week 16	Day 113	[100, 116]

*CPET may be conducted between study visits 10 and 12, therefore the planned analysis window ranges from Day 65 to Day 99 with Day 85 set to the scheduled visit day. Note: The window is adjusted for visit 12; visit 10 will not be presented.

For any subjects who discontinued treatment prior to Week 4 dose adjustment, the subjects will not be presented in the treatment columns (initial dose/adjusted dose), however will be presented in the total column in the table.

If the “seconds” portion of the date/time variable is missing or not collected, it will be imputed as “:00”, as needed.

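### The SAP's treatment-emergent window closes just before last dose + 28 days, so an adverse event that starts on the scheduled Week 16/End of Study day is left out of the TEAE tables

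*SAP*

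**What the plan says.** SAP 9.1 gives four routes to treatment emergence. For a new event, the AE qualifies if it "begins on or after the first dose of study drug and before the stop of study drug + 28 days". For an event already present, it qualifies if it "begins before the first dose of study drug and worsens in severity on or after the first dose of study drug and before the" same limit. The other two routes deal with missing dates.

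Protocol 11.3.8.1 has a start and no end. It covers "AEs with onset on or after the first dose of study medication, or with an onset before the first dose of study medication" that becomes more severe on or after that dose.

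Three other places fix the calendar and the collection period:

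- **Dosing.** Protocol 9.2.1: "At all visits from Day 1 to Week 12 (inclusive), MYK-461 will be administered at the investigational site". Protocol 9.5.6 and Appendix 1 also list a dose at the Week 12 visit.
- **AE collection.** Protocol synopsis, End of Study: "All AEs, including SAEs and deaths, will be collected for the duration of the study, up to and including the EOS visit". Protocol 10.3 extends reporting of serious AEs (SAEs) to the last visit or 30 days after the last dose, whichever is later. It also asks for later SAEs that are judged related.
- **Week 16/EOS visit.** Protocol 9.5.7 includes an AE assessment and, in the same words as 9.5.6, "Hemodynamic stress echocardiography after 4 hour fast".

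SAP 9.1.4 says that every SAE will be tabulated. The list of outputs titles those tables (14.3.1.5.x) as covering serious treatment-emergent events only.

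**The concern.** The tables by system organ class, relationship and severity are all restricted to treatment-emergent AEs (TEAEs). They are the main output for the safety and tolerability objective. A limit of 28 days after last dose, with equality excluded, coincides with a four-week washout and so removes the visit that closes it. That visit is a planned AE-collection point and includes a symptom-limited exercise test.

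Nor is the EOS day clearly free of drug. Protocol 1.2.1 gives a mean half-life of about 8 days after single doses in healthy men, and 28 / 8 = 3.5 half-lives.

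With about 10 subjects in each part, one subject more or less is about 10 percentage points (1/10) in that part's table.

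**Working it through.** **Inputs.** Day 1 is the day of first dose (SAP section 4). Week 12 is Day 85 and Week 16 is Day 113 (SAP section 4, visit table). L is the last-dose day, taken as the SAP's stop of study drug. E is the EOS day, and g = E − L.

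**Reproducing the SAP's days.** Scheduled day = 1 + 7 × week. Week 12: 1 + 84 = 85. Week 16: 1 + 112 = 113. Both match.

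**On schedule.** L = 85, so the limit is 85 + 28 = 113. An onset on Day 113 must satisfy 113 < 113, which is false. The last counted day is 112, so 1 day is lost: the EOS day itself.

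**The other day count.** The protocol elsewhere calls the end of Week 4 Day 28, which makes Week 12 Day 84 and Week 16 Day 112. The limit is then 84 + 28 = 112, and 112 < 112 is again false. The result does not depend on the convention.

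**General formula.** The last counted day is L + 27, so the days lost up to and including EOS are max(0, g − 27).

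**If both visits may move ±1 day** (assumption: Protocol 9.6 gives ±1 day for weekly visits and nothing specific to Weeks 12 and 16):

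| Last dose | EOS Day 112 | EOS Day 113 | EOS Day 114 |
|---|---|---|---|
| Day 84 | g = 28, lost 1 | g = 29, lost 2 | g = 30, lost 3 |
| Day 85 | g = 27, lost 0 | g = 28, lost 1 | g = 29, lost 2 |
| Day 86 | g = 26, lost 0 | g = 27, lost 0 | g = 28, lost 1 |

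The range is 0 to 3 days. In 6 of the 9 combinations the EOS day is on or after the limit. These are counts of calendar combinations, not probabilities, and days of follow-up, not event rates.

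**Checking possible limits:**

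- *On or before L + 28.* Days lost are max(0, g − 28): 0 on schedule, 0 to 2 under ±1 day.
- *Through EOS, inclusive.* This captures all AEs collected through the EOS visit. However, SAEs are reportable to L + 30 = Day 115, so on schedule Days 114 and 115 remain outside. With g = 26 the window would close at L + 26, one day earlier than the present L + 27. A subject who withdraws from all follow-up (Protocol 5.5.1) has no EOS visit to close it.
- *Later of EOS and L + 30, both inclusive.* This covers the AE collection period and the dated SAE reporting period, including subjects with an early EOS visit or none.
- *Protocol 11.3.8.1, no upper limit.* This covers all of the above, and also the late related SAEs that Protocol 10.3 asks for.

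**The case against.** The strongest reply is that an end date is legitimate and this one costs almost nothing. Protocol 11.3 describes its analyses as an outline and leaves detail to the SAP. Events reported at EOS with an earlier onset still count. SAP 9.1.1 lists all AEs, and the overview line for AEs leading to death is not limited to TEAEs. All of this stands, and it is why the point is small. It does not explain why the limit should exclude a scheduled AE-collection day.

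Two readings of the rule would soften it. If the limit were applied by clock time, an EOS-day onset before the hour of the Day 85 dose would count; but SAP 9.1 imputes dates only, so a date-level test is the natural reading. If stop of study drug meant the first day without drug, the limit would be 86 + 28 = 114 and Day 113 would count; but SAP 7.2.1 measures exposure to the last-dose date, and 9.1 gives no other meaning.

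A reader might infer more than the documents support:

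- *That the SAP contradicts its own visit windows*, because a Week 16 result dated on or after Day 113 is accepted. Section 4 ("The planned analysis visit window for weekly visits will consider +/- 3 days of the scheduled visit date") assigns results to nominal visits. It does not define treatment emergence and it is not permission for visits to move, so it is no basis for a larger loss.
- *That the undated-event rule is inconsistent*, because an AE that "is completely missing an onset date and end date" counts while one dated to EOS does not. That is a conservative rule for missing data, and it can stand beside a dated limit.
- *That early terminators lose more.* Protocol 9.5.6 lists on-site dosing under the combined Week 12/Early Termination visit, and Appendix 1 puts EOS four weeks after early termination. As written, the gap is again 28 days.
- *That the SAP's severity and causality scales are wrong* because they differ from Protocol 10.2.2. Which scale was collected depends on the case report form, which is not in the documents.

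**Conclusion.** The point holds, at low severity. Read at date level with the stop of study drug as the last-dose date, SAP 9.1 excludes onsets and worsenings on the scheduled EOS day, and it is narrower than Protocol 11.3.8.1 and the AE and SAE collection periods. The size is 1 day on schedule, and 0 to 3 days if Weeks 12 and 16 may each move by one day.

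It would be too strong to say that safety data are lost or that the primary result is at risk. The events remain in the database and in the listing of all AEs; only their place in the TEAE tables is affected. For SAEs the position is unclear, because the SAP's text promises all of them while the table titles admit only those that are treatment-emergent.

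**What to change.** In both the onset and the worsening bullet of SAP 9.1, adopt the definition in Protocol 11.3.8.1: on or after first dose, with no upper limit. If the sponsor wants a limit, set it at the later of the EOS visit (inclusive) and 30 days after last dose (inclusive), and state that the stop of study drug is the date of last dose. Changing only to on or before 28 days, or only to the EOS visit, leaves the gaps shown in the working.

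Make the text of SAP 9.1.4 and the titles of Tables 14.3.1.5.x agree. If the tables are to cover all SAEs, say how those between consent and first dose are shown. If they are to cover serious TEAEs only, change the text.

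The cost is SAP wording and, at most, table titles. No new data are needed, and TEAE counts may rise slightly.

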9.1.1. Incidence of Adverse Events

Summaries of the total number of TEAEs and the number and percentage of subjects with at least one TEAE will be provided. Treatment-emergent AEs will be presented by SOC and PT. At each level of subject summarization, a subject is counted once if the subject reported one or more events. Percentages will be calculated out of the number of subjects in the Safety set.

A summary of TEAEs will also be presented in descending order from the SOC with the highest total incidence (that is, summed across all treatment groups) to the SOC with the lowest total incidence. If the total incidence for any two or more SOC is equal, the SOC will be presented in alphabetical order. Within each SOC, the PTs will be presented in alphabetical order.

All AEs will be presented in a listing.

9.1.2. Relationship of Adverse Events to Study Drug

A summary of TEAEs by relationship to study drug will be presented in a table by incidence of occurrence. The investigator will provide an assessment of the relationship of the event to the study drug. The possible relationships are “Not Related”, “Unlikely”, “Possible”, “Probable”, and “Definite”. In the TEAE relationship table, if a subject reports multiple occurrences of the

same TEAE, only the most closely related occurrence will be presented. Treatment –emergent AEs that are missing a relationship will be presented in the summary table as “Definite” but will be presented in the data listing with a missing relationship or the actual relationship respectively. Percentages will be calculated out of the number of subjects in the Safety set.

The TEAE data will be categorized and presented by SOC, PT, and relationship in a manner similar to that described in Section 9.1.1.

9.1.3. Severity of Adverse Event

A summary of TEAEs by severity will be presented in a table. The severity that will be presented represents the most extreme severity captured on the CRF page. The possible severities are “Mild,” “Moderate,” and “Severe.” In the TEAE severity table, if a subject reported multiple occurrences of the same TEAE, only the most severe will be presented. Treatment-emergent AEs that are missing severity will be presented in tables as “Severe” but will be presented in the data listing with a missing severity. Percentages will be calculated out of the number of subjects in the Safety set.

The TEAE data will be categorized and presented by SOC, PT, and severity in a manner similar to that described in Section 9.1.1.

9.1.4. Serious Adverse Events

The seriousness of an AE should be assessed by the Investigator independently from the severity of the AE. A serious AE (SAE) is defined as any untoward medical occurrence that at any dose results in death, is life-threatening, is a congenital anomaly/birth defect, requires in-patient hospitalization or prolongation, or results in significant disability/incapacity.

Important medical events that may not result in death, be life-threatening, or require hospitalization may be considered SAEs when, based upon medical judgment, they may jeopardize the subject and may require medical or surgical intervention to prevent one of the outcomes listed above.

All SAEs will be summarized by MedDRA SOC and PT in a table.

9.1.5. Adverse Events Leading to Treatment Discontinuation

All TEAEs with a study drug action taken of “Drug Withdrawn” will be presented in a data listing.

9.1.6. Adverse Events Leading to Study Discontinuation

A summary of TEAEs where the answer to “Caused Study Discontinuation” is “Yes” will be presented in a data listing.

9.1.7. Death

All subjects who have an AE with an outcome of “Death Related to Adverse Event” will be presented in a listing.

9.2. Clinical Laboratory Evaluations

Safety laboratory data including hematology, chemistry, and urinalysis will be evaluated by visit for the Safety Analysis Population using descriptive statistics.

Laboratory assessments will be performed by a PPD central laboratory. All summaries will be based on the standard units provided by the central laboratory, no conversions will be attempted. Drug-induced liver injury (DILI) will be identified, according to the criteria in the protocol Section 7.4, and summarized. Subjects who met each of the DILI criteria, TBL > 2 X ULN or > 3 X ULN for AST/ALT with baseline < ULN will be summarized descriptively.

